#### **9.1.7. Case Report Forms**

For each subject consented, an eCRF will be completed by an authorized study staff member whose training for this function is documented according to study procedures. An eCRF should be completed on the day of the subject visit to enable the sponsor to perform central monitoring of safety data. The Eligibility Criteria eCRF should be completed only after all data related to eligibility have been received. Subsequent to data entry, a study monitor will perform SDV within the electronic data capture system. Original entries as well as any changes to data fields will be stored in the audit trail of the system. Prior to database lock (or any interim time points as described in the clinical data management plan), the investigator will use his/her log in credentials to confirm that the forms have been reviewed, and that the entries accurately reflect the information in the source documents. The eCRF capture the data required per the protocol schedule of events and procedures. System-generated or manual queries will be issued to the investigative site staff as data discrepancies are identified by the monitor or internal Gilead staff,

who routinely review the data for completeness, correctness, and consistency. The site coordinator is responsible for responding to the queries in a timely manner, within the system, either by confirming the data as correct or updating the original entry, and providing the reason for the update (eg, data entry error). At the conclusion of the study, Gilead will provide the site with a read-only archive copy of the data entered by that site. This archive must be stored in accordance with the records retention requirements outlined in Section 9.1.6.

#### **9.1.8. Investigational Medicinal Product Accountability and Return**

Where possible, study drug should be destroyed at the site. If the site has an appropriate SOP for drug destruction as determined by Gilead, the site may destroy used (empty or partially empty) and unused study drug supplies in accordance with that site's approved SOP. A copy of the site's approved SOP will be obtained for central files. If study drug is destroyed on site, the investigator must maintain accurate records for all study drug destroyed. Records must show the identification and quantity of each unit destroyed, the method of destruction, and the person who disposed of the study drug. Upon study completion, copies of the study drug accountability records must be filed at the site. Another copy will be returned to Gilead.

If the site does not have an appropriate SOP for drug destruction, used and unused study drug supplies are to be sent to the designated disposal facility for eventual destruction. The study monitor will provide instructions for return.

The study monitor will review study drug supplies and associated records at periodic intervals.

#### **9.1.9. Inspections**

The investigator will make available all source documents and other records for this study to Gilead's appointed study monitors, IRB/IECs, or to regulatory authority or health authority inspectors.

#### **9.1.10. Protocol Compliance**

The investigator is responsible for ensuring the study is conducted in accordance with the procedures and evaluations described in this protocol.

### **9.2. Sponsor Responsibilities**

#### **9.2.1. Protocol Modifications**

Protocol modifications, except those intended to reduce immediate risk to study subjects, may be made only by Gilead. The investigator must submit all protocol modifications to the IRB/IEC in accordance with local requirements and receive documented IRB/IEC approval before modifications can be implemented.

### **9.2.2. Study Report and Publications**

A clinical study report (CSR) will be prepared and provided to the regulatory agency(ies). Gilead will ensure that the CSR meets the standards set out in the ICH Guideline for Structure and Content of CSRs (ICH E3). Note that an abbreviated report may be prepared in certain cases.

Investigators in this study may communicate, orally present, or publish in scientific journals or other scholarly media only after the following conditions have been met:

the results of the study in their entirety have been publicly disclosed by or with the consent of Gilead in an abstract, manuscript, or presentation form or the study has been completed at all study sites for at least 2 years

The investigator will submit to Gilead any proposed publication or presentation along with the respective scientific journal or presentation forum at least 30 days before submission of the publication or presentation.

No such communication, presentation, or publication will include Gilead's confidential information.

The investigator will comply with Gilead's request to delete references to its confidential information (other than the study results) in any paper or presentation and agrees to withhold publication or presentation for an additional 60 days in order to obtain patent protection if deemed necessary.

### **9.3. Joint Investigator/Sponsor Responsibilities**

#### **9.3.1. Payment Reporting**

Investigators and their study staff may be asked to provide services performed under this protocol, eg, attendance at Investigator's Meetings. If required under the applicable statutory and regulatory requirements, Gilead will capture and disclose to Federal and State agencies any expenses paid or reimbursed for such services, including any clinical study payments, meal, travel expenses or reimbursements, consulting fees, and any other transfer of value.

#### **9.3.2. Access to Information for Monitoring**

In accordance with regulations and guidelines, the study monitor must have direct access to the investigator's source documentation in order to verify the accuracy of the data recorded in the CRF/eCRF.

The monitor is responsible for routine review of the CRF/eCRF at regular intervals throughout the study to verify adherence to the protocol and the completeness, consistency, and accuracy of the data being entered on them. The monitor should have access to any subject records needed to verify the entries on the CRF/eCRF. The investigator agrees to cooperate with the monitor to ensure that any problems detected through any type of monitoring (central, on site) are resolved.

### **9.3.3. Access to Information for Auditing or Inspections**

Representatives of regulatory authorities or of Gilead may conduct inspections or audits of the clinical study. If the investigator is notified of an inspection by a regulatory authority the investigator agrees to notify the Gilead medical monitor immediately. The investigator agrees to provide to representatives of a regulatory agency or Gilead access to records, facilities, and personnel for the effective conduct of any inspection or audit.

### **9.3.4. Study Discontinuation**

Both the sponsor and the investigator reserve the right to terminate the study at any time. Should this be necessary, both parties will arrange discontinuation procedures and notify the appropriate regulatory authority(ies), IRBs, and IECs. In terminating the study, Gilead and the investigator will assure that adequate consideration is given to the protection of the subjects' interests.

## 11. APPENDICES

- Appendix 1. Investigator Signature Page
- Appendix 2. Study Procedures Table
- Appendix 3. Tumor Specific Inclusion/Exclusion Criteria
- Appendix 4. NCI-CTCAE Grading Scale for Severity of Adverse Events and Laboratory Abnormalities
- Appendix 5. Pregnancy Precautions, Definition for Female of Childbearing Potential, and Contraceptive Requirements
- Appendix 6. Response Evaluation Criteria in Solid Tumors (RECIST Version 1.1)
- Appendix 7. Response Assessment for Classic Hodgkin Lymphoma (Lugano Classification)
- Appendix 8. Pandemic Risk Assessment and Mitigation Plan

**Appendix 2. Study Procedures Table**

Study Phase Cycle Day	Screening Day -28 to Day 1	Cycle 1 (First 21 Days)						C2D1	C3D1	C4D1	C5D1	Every 3 weeks	Every 6 weeks	Every 9 weeks	EOT f	30 day Safety Follow-up f
		Cycle 1 Day 1	Day 2	Day 4	Day 8	Day 11	Day 15									
Window (day)	-28	±0	±0	±0	±1	±1	±2	±2	±2	±2	±2	±7	±7	±7	±7	±7
Informed Consent	X															
Medical and Medication History a	X															
Physical Examination b	X	X	X	X	X	X	X	X	X	X	X	X			X	
Vital Signs c	X	X	X	X	X	X	X	X	X	X	X	X			X	
12 lead ECG d	X	X			X		X	X	X	X	X	X d			X	X
Adverse events/ Concomitant medications e	X	X	X	X	X	X	X	X	X	X	X	X			X	X
Study Drug Dispensing		X						X	X	X	X	X				
Dosing Diary Accountability		X	X	X	X	X	X	X	X	X	X	X				
IXRS Registration	X	X						X	X	X	X	X			X	
CBC with differential	X g	X		X	X	X	X	X	X	X	X	X			X	
Coagulation	X g	X		X	X	X	X	X	X	X	X	X			X	
Chemistry	X g	X		X	X	X	X	X	X	X	X	X			X	
TSH		X											X			
Basal Cortisol		X											X			
Urinalysis		X			X			X	X	X	X	X			X	
Pregnancy Test h	X	X						X	X	X	X	X			X	

Study Phase Cycle Day	Screening Day -28 to Day 1	Cycle 1 (First 21 Days)						C2D1	C3D1	C4D1	C5D1	Every 3 weeks	Every 6 weeks	Every 9 weeks	EOT f	30 day Safety Follow-up f
		Cycle 1 Day 1	Day 2	Day 4	Day 8	Day 11	Day 15									
Window (day)	-28	±0	±0	±0	±1	±1	±2	±2	±2	±2	±2	±7	±7	±7	±7	±7
HIV/CD4+/HBV/HCV Testing i	X															
<h1 style="margin: 0;">CCI</h1>																
<h1 style="margin: 0;">CCI</h1>																
<h1 style="margin: 0;">CCI</h1>																
<h1 style="margin: 0;">CCI</h1>																
<h1 style="margin: 0;">CCI</h1>																
<h1 style="margin: 0;">CCI</h1>																
<h1 style="margin: 0;">CCI</h1>																
Tumor PD L1 IHC p	X															
Archival Tumor Tissue or pre treatment biopsy q	X															

Study Phase Cycle Day	Screening Day -28 to Day 1	Cycle 1 (First 21 Days)						C2D1	C3D1	C4D1	C5D1	Every 3 weeks	Every 6 weeks	Every 9 weeks	EOT f	30 day Safety Follow-up f
		Cycle 1 Day 1	Day 2	Day 4	Day 8	Day 11	Day 15									
Window (day)	-28	±0	±0	±0	±1	±1	±2	±2	±2	±2	±2	±7	±7	±7	±7	±7
CCI																
CCI																
CT Scan with Contrast or MRI e	X								X		X			X	X s	
PET CT u	X								X		X					
ECOG Performance Status	X	X			X		X								X	

- a Medical history includes significant past medical events (eg, prior hospitalizations or surgeries), a review of the disease under study, prior anti cancer therapies, and any concurrent medical illnesses.
- b Screening and end of treatment Physical Examinations will be a complete physical examination. Beginning on C1D1, a modified physical examination will be performed to monitor for any changes (eg, lymph nodes, lung, cardiac, abdomen, skin, neurologic, and any systems, as clinically indicated). Weight (without shoes) should be measured at each PE. Height (without shoes) should be measured at screening only.
- c Vital signs will be taken within 15 min pre GS 4224 dose. C1D1 vitals will also be collected at 2 and 4 hours postdose (± 15 min); vital signs will be taken predose only at all subsequent visits.
- d A triplicate 12 lead ECG will be collected at screening, at predose on Cycle 1 Day 1, Cycle 1 Day 8, 1.5 hours postdose (± 9 min) on Cycle 1 Days 1 and 15, at the EOT visit and at the 30 Day Safety Follow up visit. Triplicate ECGs should be taken 5 minutes apart. Single 12 lead ECGs will be collected predose on Day 1 of Cycles 2 6.
- e Adverse events will be assessed at pre and post GS 4224 dosing during applicable clinic visits. Subjects will also return to clinic at 30 day after last study drug dose, to assess AEs and SAEs. If the subject cannot return to the clinic, the site will contact the study subject by phone approximately 30 days after the last dose of study drug to assess AEs.
- f End of treatment (EOT) and 30 day follow up visit are to be done 30 days after last dose of GS 4224. Subjects who miss the 30 day Safety follow up visit will be contacted by phone 30 days (± 7 days) after the last dose to assess AEs.
- g Screening chemistry, hematology, and coagulation to be collected within 10 days of Study Day 1/C1D1.
- h If applicable (females of child bearing potential). Serum pregnancy will be conducted at screening. Urine pregnancy will be conducted predose on Day 1 of each cycle and at EOT.
- i HIV, HBsAg, and HCV antibody viral testing in subjects with current or prior history of HIV, HBV, and HCV infection, respectively. CD4+ count will also be performed in subjects with current or prior history of HIV.

[REDACTED]

p Where required for enrollment and if not already known, PD L1 expression will be determined.  
q Archival tumor tissue for biomarker analysis will be collected. The tissue should preferably be obtained either at the time of or after the diagnosis of advanced disease has been made and from a site not previously irradiated. Tissue must be collected between screening and Cycle 2. If archival tissue is not available, a pre treatment biopsy will be collected from enrolled subjects. For the 1000 mg BID dose escalation cohort, subjects with melanoma, Merkel cell, MSI H cancers, and classical Hodgkin lymphoma are not required to have archival or fresh biopsy tissue

[REDACTED]

t Tumor evaluation by CT/MRI will be performed during screening (within 28 days of Day 1) and every 6 weeks for the first 2 scans and then every 9 weeks. A baseline scan within 6 weeks of Day 1 is acceptable. Cycle 3 Day 1 and Cycle 5 Day 1 scans can have a 7 day window. The same radiographic procedure used to define measurable lesions must be used throughout the study for each subject.  
u PET CT to be completed at screening (within 28 days of Day 1), Cycle 3 Day 1, and Cycle 5 Day 1 only for subjects with cHL. Per Lugano 2014 criteria, PET CT is required to confirm radiographic CR in subjects with bone marrow involvement at screening. In subjects with bone marrow involvement at screening and at a time point where CR is suspected, PET CT will be required to confirm CR if CR was not achieved at Cycle 3 and/or 5.

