**Treatment:**

Subjects who meet eligibility criteria will receive GS-4224 orally once daily in the 400 1500 mg QD cohorts and 1000 mg twice daily in the 1000 mg BID cohort (separated by approximately 12 hours). Each cycle will consist of 21 days. Safety and efficacy assessments will occur on an outpatient basis including assessment of tumor response, physical exam, vitals, ECG, collection of blood samples (for routine safety labs, GS-4224 PK, pharmacodynamic markers, and other biomarkers at applicable visits), urine pregnancy test (every 3 weeks while receiving GS-4224 in females of childbearing potential), and assessment of AEs. In addition, subjects will undergo postbaseline CT/MRI and PET-CT (for cHL) scans for tumor response assessment. A subject who does not show evidence of disease progression by clinical assessment or by CT/MRI or applicable scan may continue receiving study treatment until disease progression (clinical or radiographic), unacceptable toxicity, withdrawal of consent, or other reasons specified in Section 3.5.

After discontinuation of all study treatment, subjects will be followed for safety for 30 days.

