**Table 5-5. Endocrine irAE Management Algorithm**

Endocrine irAEs		
Endocrine Disorder	Management	Follow Up
Asymptomatic TSH abnormality	Continue GS-4224 therapy per protocol. If TSH < 0.5 × lower limit of normal (LLN) or TSH > 2 × ULN, or consistently out of range in 2 subsequent measurements: Include free thyroxine at subsequent cycles as clinically indicated; consider endocrinology consult.	
Symptomatic endocrinopathy	Evaluate endocrine function. Consider pituitary scan. Symptomatic with abnormal lab/pituitary scan: Interrupt GS-4224 therapy per protocol; 1-2 mg/kg/day methylprednisolone IV or oral equivalent; initiate appropriate hormone therapy No abnormal lab/pituitary MRI scan but symptoms persist: Repeat labs in 1-3 weeks, MRI in 1 month.	If improves (with or without hormone replacement): Taper corticosteroids over ≥ 1 month and consider prophylactic antibiotics for opportunistic infections. Resume GS-4224 therapy per protocol. Subjects with adrenal insufficiency may need to continue corticosteroids with mineralocorticoid component.
Suspicion of adrenal crisis (eg, severe dehydration, hypotension, shock out of proportion to current illness)	Interrupt or discontinue GS-4224 therapy per protocol Rule out sepsis Stress dose of IV corticosteroids with mineralocorticoid activity IV fluids Consult endocrinologist If adrenal crisis ruled out, treat as above for symptomatic endocrinopathy	

irAE immune related adverse event; IV intravenous(ly); LLN lower limit of normal; MRI magnetic resonance imaging; TSH thyroid stimulating hormone; ULN upper limit of normal

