**Table 6-1. Analytes**

Chemistry	Urinalysis	Hematology	Other
Albumin	Color and appearance	WBC and differential count	Serum β–hCG or urine pregnancy test c Endocrine Function Tests TSH and freeT4 d Basal cortisol HIV, HBsAg, and HCV antibody viral testing in subjects with current or prior history of HIV, HBV, and HCV infection, respectively. b CD4+ count will also be performed in subjects with current or prior history of HIV.
Alkaline phosphatase	Specific gravity	Hemoglobin	
ALT	pH	Hematocrit	
AST	Occult blood	Platelet count	
Bicarbonate	Protein	ANC	
BUN/total urea	Glucose	MCH	
Calcium	Bilirubin	MCHC	
Chloride	Leukocyte esterase	MCV	
Serum Creatinine a	Nitrite	RBC	
GGT	Urobilinogen	Differential	
Glucose	Ketones	Eosinophils	
LDH	Microscopic b	Lymphocytes	
Lipase		Monocytes	
Cholesterol		Neutrophils	
Triglycerides		Coagulation	
Amylase		Prothrombin time (INR)	
Magnesium		aPTT	
Phosphorus/phosphates			
Potassium			
Sodium			
Total bilirubin b			
Direct bilirubin			
Total protein			

β hCG beta human chorionic gonadotropin; ALT alanine aminotransferase; ANC absolute neutrophil count; aPTT activated partial thromboplastin time; AST aspartate aminotransferase; BUN blood urea nitrogen; CD4+ cluster determinant 4 positive; Free T4 free thyroxine; GGT gamma glutamyltransferase; HBsAg hepatitis B surface antigen; HBV hepatitis B virus; HCV hepatitis C virus; HIV human immunodeficiency virus; INR international normalized ratio; LDH lactate dehydrogenase; MCH mean corpuscular hemoglobin; MCHC mean corpuscular hemoglobin concentration; MCV mean corpuscular volume; RBC red blood cell; TSH thyroid stimulating hormone; WBC white blood cell

a Estimated creatinine clearance (CLcr)/glomerular filtration rate will be calculated based on the Cockcroft Gault formula using actual body weight: CLcr (mL/min) (140 age [years])\* weight (kg) / (serum creatinine [mg/dL]\*72). If the subject is female, multiply the quantity by 0.85.

b Reflex testing based on other abnormalities

c Females of childbearing potential only. Serum pregnancy will be conducted at screening within 72 h of first treatment dose (if performed earlier in screening period then a urine pregnancy test may be performed prior to first dose); urine pregnancy test performed at all other indicated visits.

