## **6.8. Posttreatment Assessments**

### **6.8.1. End of Treatment Visits**

The EOT visit requirements are outlined in [Appendix 2](#). There is an EOT visit and a 30-day follow-up visit, which occurs 30 days ( $\pm 7$  days) after last dose of study treatment.

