### 8.7.3. Laboratory Evaluations

Selected laboratory data will be summarized based on observed data. Data and change from baseline at all scheduled time points will be summarized. The focus of laboratory data summarization will be on treatment-emergent laboratory abnormalities. A treatment-emergent laboratory abnormality is defined as an abnormality that, compared to baseline, worsens by  $\geq 1$  grade in the period from the first dose of study drug to 30 days after the last dose of study treatment. If baseline data are missing, then any graded abnormality (ie, an abnormality that is Grade  $\geq 1$  in severity) will be considered treatment emergent.

Graded laboratory abnormalities will be defined using the NCI-CTCAE version 5.0 when applicable. Summary tables will be presented for each relevant assay to show the number of subjects by CTCAE severity grade with corresponding percentages. For parameters for which a CTCAE scale does not exist, the frequency of subjects with values below, within, and above the normal ranges will be summarized. Subjects will be characterized only once for a given assay, based on their worst severity grade observed during a period of interest (eg, during the study or from baseline to a particular visit).

Shift tables for selected laboratory data may also be presented by showing change in CTCAE severity grade from baseline to the worst grade after baseline. For parameters for which a CTCAE scale does not exist, shift tables presented will show change in results from baseline to the worst grade after baseline. Separate listings and summaries will be prepared for laboratory abnormalities that are Grade  $\geq 3$  in severity.

CCI

[Redacted]

CCI

[Redacted]

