7.2.1.2. Summaries of Laboratory Abnormalities

The following summaries (number and percentage of subjects) for treatment-emergent laboratory abnormalities will be provided by lab test and cohort; subjects will be categorized according to the most severe postbaseline abnormality grade for a given lab test:

- TE laboratory abnormalities

In the summary of laboratory abnormalities, the denominator is the number of subjects with nonmissing postbaseline values up to 30 days after last dosing date.

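### TSH and basal cortisol are scheduled six-weekly from an unstated start and not at end of treatment, so early leavers have no scheduled post-baseline endocrine value

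*Protocol*

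**What the plan says.** In the study procedures table (Protocol Appendix 2), the TSH row and the "Basal Cortisol" row each carry two marks: C1D1 and the six-weekly column. Screening, C2D1 to C5D1, EOT and the 30-day follow-up are blank. Neither row has a footnote marker, so no redacted footnote alters them.

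Table 6-1 lists these assays apart from chemistry, in its last column, under "Endocrine Function Tests TSH and freeT4" and basal cortisol. The chemistry draw at EOT therefore does not supply them. Section 6.8.1 leaves the content of that visit to the same table: "The EOT visit requirements are outlined in" Appendix 2.

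On analysis, Protocol 8.7.3 says that for tests without a CTCAE scale "the frequency of subjects with values below, within, and above the normal ranges will be summarized". SAP 7.2.1.2 tabulates treatment-emergent laboratory abnormalities by test and cohort, and there "the denominator is the number of subjects with nonmissing postbaseline values up to 30 days after last dosing date". SAP 7.2 names endocrine tests in a by-subject listing.

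**The concern.** The schedule leaves two things open. The first is when on-treatment endocrine testing begins. Two sites could follow the same table and take the first sample 12 weeks apart (Week 6 or Week 18).

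The second is what happens to subjects who leave before that sample. They include subjects who stop for toxicity, and the plan schedules no endocrine test at their last visit. Any cohort frequency of abnormal TSH or cortisol then describes those who stayed long enough to be tested.

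Asymptomatic abnormalities matter most, because symptoms cannot prompt the test. The asymptomatic-TSH row of Table 5-5 works only from laboratory results ("Include free thyroxine at subsequent cycles as clinically indicated; consider endocrinology consult"), so it depends on a sample having been taken.

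**Working it through.** The plan states no figure on this point to reproduce. The check compares rows of the table, converts visits to days, and sizes the gap under stated assumptions.

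**1. Marks in Appendix 2**

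| Row | C2D1 | C3D1 | C4D1 | C5D1 | Periodic column | EOT |
|---|---|---|---|---|---|---|
| CBC, coagulation, chemistry, urinalysis | X | X | X | X | 3-weekly | X |
| CT/MRI | – | X | – | X | 9-weekly | X |
| TSH, basal cortisol | – | – | – | – | 6-weekly | – |

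**2. Days of the first test.** The Protocol synopsis gives the cycle length: "Each cycle will consist of 21 days". So CnD1 falls on Day 21(n − 1) + 1: C3D1 is Day 43 and C5D1 is Day 85. As a check, the scan rule in footnote t ("every 6 weeks for the first 2 scans and then every 9 weeks") gives Days 1 + 42 = 43 and 1 + 84 = 85, which are the two visits marked in the CT row.

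- Six-weekly counted from C1D1: Day 43, then Day 85. With the ±7-day window, the first test falls on Days 36–50.
- Six-weekly starting after C5D1: Day 85 + 42 = 127 (Week 18). With the window, Days 120–134.

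On either reading no endocrine test is scheduled inside the 21-day DLT window. On the second, none falls within the 90 days of dosing that Protocol 3.2.1.2 considers for the RP2D; on the first, Days 43 and 85 both do.

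**3. Share stopping before the first test.** Assume exponential time on drug with median m weeks. The share stopping before week w is 1 − 2^(−w/m).

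| Median (weeks) | Before Week 6 | Before Week 18 |
|---|---|---|
| 6 | 50% | 87.5% |
| 9 | 37% | 75% |
| 12 | 29% | 65% |
| 18 | 21% | 50% |

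The medians are chosen for illustration.

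**4. Effect on a cohort summary.** Take the 20-subject maximum of the 1000 mg BID cohort and assume that 30% stop before the first test and are not tested off schedule. Then 20 × 0.7 = 14 subjects have a value. With no abnormal results, the exact two-sided 95% upper limit is 1 − 0.025^(1/n): 16.8% at n = 20 and 23.2% at n = 14.

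Time on drug also sets the number of tests. At an assumed, independent 5% chance of an abnormal result per test, the chance of at least one is 1 − 0.95^k: 5.0%, 9.8% and 18.5% for 1, 2 and 4 tests.

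**5. EOT timing.** Appendix 2 footnote f puts EOT 30 days after the last dose, and the table allows ±7 days. Section 6.8.1.1 puts it at discontinuation, while also allowing it to coincide with the 30-day visit. SAP 7.2.1.1 counts laboratory values up to the last dose plus 30 days. Under footnote f an EOT sample could be taken as late as 30 + 7 = 37 days after the last dose, outside that window.

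**The case against.** Four stronger readings are tempting, and the documents do not support them.

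- **Testing is skipped until after C5D1.** The blank cells do not establish this. A row marked at C1D1 and then six-weekly can at least as naturally mean C3D1 and C5D1. The CT row is a weak analogy, because its interval changes after two scans and so needs separate marks. The chemistry row keeps the Week 18 reading possible, but no more than that.
- **Early leavers are never tested on drug.** Protocol 6.4 allows unscheduled visits and collects their data. SAP 3.8.2 counts unscheduled results toward the worst post-baseline grade. Table 5-5 calls for endocrine evaluation when there are symptoms. Only a scheduled value is missing.
- **Cohorts with shorter treatment look cleaner because untested subjects count as normal.** SAP 7.2.1.2 excludes them from the denominator. What remains is selection toward those who stayed and fewer tests per subject. The SAP also tabulates exposure by cohort (4.2.2), which lets a reader see this.
- **Endocrine safety as a whole, or dose finding, is compromised.** Adverse events are collected to 30 days after the last dose whatever the laboratory schedule (Protocol 7.3.2). The DLT and MTD rules use Days 1–21, which neither reading changes.

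Two further points stand. The SAP names endocrine tests only in a listing and specifies no below/within/above-range table, although SAP 7.7 declares no departure from the protocol's safety analyses; how far a rate will be reported is therefore unclear. And the study stopped in Phase 1b with only descriptive analysis for a synoptic report, which limits the practical weight.

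**Conclusion.** The point holds as a gap in scheduled data collection. The start of the six-weekly interval is undefined, and no endocrine test is marked at EOT. A subject who stops before the first six-weekly test has no scheduled post-baseline TSH or cortisol and, unless tested off schedule, leaves the laboratory denominator. The loss falls on laboratory-detected abnormalities, asymptomatic ones above all.

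The documents do not give the share affected. With exponential time on drug and medians of 6 to 18 weeks, it is 21% to 50% for a first test at Week 6. The Week 18 figures apply only if the column starts after C5D1, which the text neither states nor excludes. Sample size and the primary endpoint are unaffected. This is a worthwhile, inexpensive improvement, not a flaw that undermines the study.

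**What to change.** 1. Add TSH and basal cortisol to the EOT column of Appendix 2, on the blood draw already taken there. SAP 3.8.2 already assigns EOT data to the next scheduled visit for subjects who discontinue treatment early, so it has a place for the value. The cost is two extra assays per subject and no new visit.
2. Reconcile the table so that the visits meant by the six-weekly column are marked. This is clarification only.
3. Reconcile footnote f with Section 6.8.1.1 on when EOT takes place, so that the EOT value falls within the 30-day treatment-emergent window.

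No separate reporting change is needed: Protocol 8.4 already asks for the number of subjects with data, and the SAP denominator is restricted to them. With Phase 2 not started, the schedule change helps subjects still on treatment and any later use of this schedule.
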